### 8.7.1 Adverse Event Reporting in eCRF

Complete and accurate data on all AEs experienced for the duration of the reporting period, will be reported on an ongoing basis in the AE pages of the eCRF.

It is important that each AE report include a description of the event, whether it is considered serious, its duration (onset and resolution dates), its severity, its relationship to the IMP, any other potential causality factors, any treatment given or other action taken (including dose modification or discontinuation of the IMP) and its outcome.

Additional guidance can be found in the eCRF Completion Guidelines provided by the Contract Research Organization (CRO).

### 8.7.2 Reporting mechanism to sponsor, Ethics Committees and Regulatory Authorities

If any SAE/SUSAR occurs, the investigators will take appropriate action immediately and will strive to identify the causes of the events. Any SAE/SUSAR will be notified by the PI to the MMV Medical Director or delegate, see Figure 1.

Any SAE/SUSAR will be notified by the Investigator to the MMV Medical Director, and to the pharmacovigilance provider (Prime Vigilance) within 24 hours by email or fax.

- MMV Senior Medical Director: [name] [name], MD
  - Email: [[contact]](mailto:[contact])
  - Tel: [name]
- Prime Vigilance Contact :
  - e-mail: [[contact]](mailto:[contact])
  - Back up [contact]

The initial report will be followed up by a full written report within three working days or five calendar days, whichever comes first, unless no further information is available. When new information becomes available a follow-up report will be provided as soon as possible. Further follow-up reports will be provided as and when new information becomes available. Photocopies of results, consultant report(s), a summary of the outcome of the reaction and the Investigator's opinion of IMP relationship to the SAE/SUSAR will accompany the SAE form if and when available.

[figure not shown]
The Sponsor will also perform an evaluation of the seriousness, causality and expectedness of all SAEs. All SAEs judged by either the Investigator or the Sponsor as having a reasonable suspected causal relationship to an IMP (i.e. definitively, probably or possibly related) will qualify as serious adverse reactions. If the Sponsor disagrees with the Investigator's causality assessment, both the opinion of the Investigator and the Sponsor are provided with the report.

All SAEs will be included in the safety/pharmacovigilance database.

All SAEs including SUSARs that are fatal or life-threatening should be reported to a Competent Authority and Ethics Committees within 24 hours followed by a complete report within 7 additional calendar days of their occurrence. All other SAEs and SUSARs that are not fatal or life-threatening must be filed as soon as possible but no later than 14 calendar days after first knowledge by the Sponsor.

Annual safety reporting to the national Competent Authority and the Ethics Committee will be in agreement with ICH guideline E2F "Note for guidance on development safety update reports (DSUR)".

**Figure 1. Safety reporting mechanism to the sponsor, TMDA, NaTHREC and IHI-IRB.**

In addition, any other safety issue which may alter the current benefit–risk assessment of the IMP will be reported by the Sponsor (or delegate) on an expedited basis to Health Authorities, Ethics Committees and the Investigator.

## 8.8 Follow-up observation for study participants with adverse reactions

All AEs must be documented and followed up until the event is either resolved or a satisfactory explanation is found, or the investigator considers it medically justifiable to terminate the follow-up.

Spontaneously reported SAEs will be collected until 30 days following the final study visit. SAEs experienced after this 30-day period will only be reported if the investigator suspects a causal relationship with the study drug.

If a study participant experiences a clinically significant finding or a worsening of an ongoing medical condition after signing the Informed Consent, the event will be recorded as an adverse event.

Any AEs that are unresolved at the participant's last AE assessment in the study (i.e. at the follow up visit) are to be followed up by the Investigator for as long as medically indicated. MMV retains the right to request additional information for any participant with ongoing AE(s)/SAE(s) at the end of the study, if judged necessary.

The Investigator will decide on

- Study drug discontinued
- Healthy participant withdrawn from study
- Concomitant Medication required
- Hospitalization required or prolonged (this should also be reported as an SAE)
- Other

The PI or delegate will follow up all AEs wherever possible until the symptom has resolved or stabilised. The date of confirming outcome will be recorded. The course of AEs will be assessed by reference to the following as a guide.

- Recovered: The AE has resolved and the participant returned to his condition prior to onset.
- Recovered with sequelae: The AE resolved, but the participant has sequelae.
- Recovering: The AE has almost resolved and the participant is returning to his condition prior to onset.
- Death: The study participant died. Causal relationship is no object.
- Ongoing: Even on the final day of observation the AE had not resolved and the participant's condition remained unchanged. In case of death, the participant died of other causes not related to the AE from which there was no recovery.

### **8.8.1 Pregnancy follow-up**

Through the Informed Consent Process all female participants will be instructed to immediately inform the Investigator if they become pregnant during the study or within the following 3 months after the last dosing and that, pregnancy should be followed through delivery or termination of the pregnancy.

A Pregnancy Form will be completed by the Investigator and submitted to the MMV Study Medical Director and Prime Vigilance preferably within 24 hours after the Investigator becomes aware of the pregnancy. The event of pregnancy itself should not be recorded on the Adverse Event Section of the eCRF. The Investigator will provide counselling to the pregnant participant about the risks of the pregnancy and the possible effects on the fetus and thereafter, she will be asked to give written consent to allow for follow up and further collection of data on her pregnancy and the outcome of the child.

Monitoring of the participant should continue until conclusion of the pregnancy. Any SAEs associated with the pregnancy (e.g., an event in the fetus, an event in the mother during or after the pregnancy, or a congenital anomaly or birth defect in the child, spontaneous abortion) will be reported on the Adverse Event Section of the eCRF if the database has not been locked at that time point. In addition, the updated Pregnancy Form will be regularly submitted with latest information on the course and outcome of the pregnancy as becomes available. The investigator should ensure that the new-born undergoes a thorough clinical investigation within the first 4 weeks after birth and that this assessment is thoroughly documented and submitted on a Pregnancy Form to the Sponsor.

Male participants may continue in the trial if pregnancy of their female partner occurs. A Pregnancy Form will be completed and submitted to the MMV Study Medical Director and Prime Vigilance preferably within 24 hours after the Investigator becomes aware of the pregnancy.

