### **2.1.3 Mechanism of action, clearance and pharmacokinetics**

PQP's mechanism of action is unknown, but it likely mirrors that of chloroquine, a close structural analogue. Chloroquine binds to toxic haem (derived from the patient's haemoglobin) within the malaria parasite, preventing its detoxification via a polymerisation step (10) PQP is a highly lipophilic compound, is highly bound to proteins (>99%) and tends to accumulate in red blood cells. In humans, PQP has a Tmax of approximately five hours after hard tablet administration. PQP is mainly metabolized by CYP3A4 and to a lesser extent by CYP2C9 and CYP2C19. PQP is also a CYP3A4 inhibitor, and a clinical study of Eurartesim® with midazolam showed a modest increase in the exposure of midazolam (<two-fold)(10). The terminal elimination half-life of PQP is around 22 days for adult patients.

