## 4 STUDY DESIGN

This is a randomized, open label, parallel-design study to evaluate the PK profile and relative bioavailability of single dose of a PQP oral granule formulation dispersed in water (test) as compared to the PQP hard tablet formulation (reference) in fasting conditions (Part 1) and to assess the BA/FE of the PQP dispersible granules formulation when administered with different food restrictions (Part 2) among African participants residing in Tanzania, in Bagamoyo Town and surrounding areas. A total of sixty (60) healthy adult participants (male and female) will be enrolled in Part 1 and Part 2.

- **Part 1:** PQP tablet / dispersible granule administered in **fasting condition** of at least 10 hours
  - Group 1: PQP hard tablet, 320 mg (N=12)
  - Group 2: PQP dispersible granule, 320 mg (N=12)
- **Transition to Part 2:**
  - To minimize the risk to healthy participants, a decision on transitioning from Part 1 to Part 2, will be taken by the Safety Review Committee (SRC) see Section 13.7, based on the safety and preliminary PK interim report of the granule formulation, compared to the PQP hard tablet, with safety data obtained up to Day 15 and PK data obtained up to Day 8. If necessary, doses may be readjusted for the Part 2 in order to assess the food effect. Description for the rationale and oversight related to the potential for dose adjustment is provided in Section 2.2.
- **Part 2:** PQP dispersible granule administered in **fed conditions (planned as 320 mg)**
  - Group 3: High-fat meal (N=12)
  - Group 4: Low-fat meal representative of African diet (N=12)
  - Group 5: Whole milk 250 ml (N=12)

In summary: Participants will be screened within a window of  $\leq$  45 days prior to in-house admission on Day -1. Each participant will be admitted to the trial unit on Day -1, and after a new eligibility check, will receive a single dose of PQP on Day 1 and will be discharged on Day 3 (a total 4 in-house days). Participants will attend the trial unit clinic for outpatient visits on Days 8, 15, 22 and 30. Details of procedures and parameters to be assessed at each study time points are outlined in Section 7 (Study Assessments and Visits) and summarized in Section 4.4 (Schedule of events).

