### **5.2.1 Inclusion criteria**

Participants must fulfil all of the following criteria to be eligible for enrolment in this trial:

1. Female or Male aged  $\geq 18$  years to  $\leq 55$  years at the date of signing informed consent.
2. Ability to provide written, personally signed, and dated informed consent to participate in the trial, in accordance with the ICH Good Clinical Practice (GCP) and applicable regulations, before any trial-related procedures.
3. An understanding, ability, and willingness to fully comply with trial procedures and restrictions.
4. Female participants must agree to follow contraceptive requirements as indicated in Section 13.2.2, from at least 30 days prior to first dosage to 16 weeks after last dosage.
5. Agrees not to donate sperm or ova from the time of the first administration of trial medication until twelve weeks after the end of the systemic exposure of the trial drug.
6. Participants must have a body weight of 50 kg or greater and a BMI between  $18.0 \text{ kg/m}^2$  -  $30.0 \text{ kg/m}^2$  (inclusive) at screening.
7. Satisfactory medical assessment with no clinically significant or relevant abnormalities as determined by; medical history, physical examination, vital signs, 12-lead ECG and clinical laboratory evaluation that is reasonably likely to interfere with the participant's participation in or ability to complete the trial as assessed by the Investigator.

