### **7.3.3 Clinic follow-up visits**

#### **7.3.3.1 Days 5, 8, 15, 22 and 30**

Vital signs, ECGs and laboratory (safety and PK Samples) and AE review:

- Procedures will be performed on a strict schedule (see Section 4.4 Schedule of events)
- End of study (i.e. Day 30).

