#### 13.2.2 Birth control and pregnancy testing

Target group for birth control	Contraception required
Female participants of non-childbearing potential (WONCBP): Defined as either postmenopausal (evidence of menopause based on a combination of amenorrhea for at least one year and increased serum follicle-stimulating hormone (FSH) level ( $>30$ IU/L), or surgical sterilisation (evidence of hysterectomy and/or bilateral oophorectomy)	None
Female participants of childbearing potential (WOCBP)	Reliable contraception in accordance with the Tanzania Clinical Trial Guidelines ( https://www.tmda.go.tz/ ), must start one complete menstrual cycle prior to the first day of dosing and continue until 16 weeks after the IMP administration (to cover a full menstrual cycle of 30 days starting after 5 half-lives of last dose of IMP).  Note: Highly effective birth control methods include: combined (estrogen and progestogen containing) oral/intravaginal/transdermal hormonal contraception associated with inhibition of ovulation, progestogen-only oral/injectable/implantable hormonal contraception associated with inhibition of ovulation, intrauterine device, intrauterine hormone-releasing system, bilateral tubal occlusion, vasectomised partner or sexual abstinence.

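### Women are told to report a pregnancy for 3 months after dosing but must use contraception for 16 weeks, so about the last 3 weeks of the precaution period go unprompted.

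*Protocol*

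**What the plan says.** **Reporting.** Under Protocol Section 8.8.1, female participants are told during the consent process to inform the investigator immediately "if they become pregnant during the study or within the following 3 months after the last dosing". The Pregnancy Form is due, preferably within 24 hours, once the investigator becomes aware of the pregnancy. No latest date is set for the form, the follow-up to outcome or the newborn examination.

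**Contraception.** Inclusion criterion 4 (Section 5.2.1, repeated in the Synopsis) requires it "from at least 30 days prior to first dosage to 16 weeks after last dosage". Section 13.2.2 tells women of childbearing potential to "continue until 16 weeks after the IMP administration", and gives the purpose as "to cover a full menstrual cycle of 30 days starting after 5 half-lives of last dose of IMP".

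**Half-life.** Section 2.1.3 states: "The terminal elimination half-life of PQP is around 22 days for adult patients".

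**Timing.** Section 4 says that each participant "will receive a single dose of PQP on Day 1 and will be discharged on Day 3". Section 7.3.3.1 puts the end of study at Day 30. The SAP lists pregnancy test results but does not deal with pregnancy follow-up.

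**The concern.** The contraception period marks how long the protocol treats a conception as a matter for precaution. One would expect the instruction to report a conception to last at least as long, and it stops earlier. A woman who conceives in week 14, 15 or 16 has had a contraception failure inside that period, yet nothing in Section 8.8.1 asks her to tell the site.

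Scheduled contact has also ended. The last visit is on Day 30, the adverse event window in Section 8.6 closes at the last visit or last planned data collection, and Section 8.8.1 says that a pregnancy is not itself recorded as an adverse event. In practice the site would learn of such a pregnancy mainly if the woman volunteered it.

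What is at stake is the completeness of a small body of safety data. The background presents piperaquine as a potential option for chemoprevention in pregnant women and women of childbearing potential, and relies on the absence of a teratogenic signal. The PK endpoints, their analysis and the scheduled safety assessments are not affected.

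**Working it through.** **Inputs**
- Reporting period for women: 3 months after the last dosing (Section 8.8.1).
- Contraception period: 16 weeks after dosing (Sections 5.2.1 and 13.2.2).
- Stated reason for 16 weeks: 5 half-lives plus a 30-day cycle (Section 13.2.2).
- Half-life: about 22 days (Section 2.1.3).
- One dose on Day 1 (Section 4); end of study on Day 30 (Section 7.3.3.1).

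**Step 1. The plan's own figure.** 5 × 22 = 110 days; 110 + 30 = 140 days; 140 / 7 = 20 weeks. The plan states 16 × 7 = 112 days. The stated reason therefore does not reproduce the stated period: 112 days is 5 half-lives with 2 days over, and a full 30-day cycle on top would fit only if the half-life were (112 − 30) / 5 = 16.4 days.

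**Step 2. The gap between the two periods.** With one dose, the last dosing is Day 1 and both periods start there. Three calendar months are 90 to 92 days.
- Gap: 112 − 92 = 20 days to 112 − 90 = 22 days, about 3 weeks.
- Share of the contraception period: 20/112 = 18% to 22/112 = 20%.
- Against the 140 days implied by the stated reason: 140 − 92 = 48 to 140 − 90 = 50 days, about 7 weeks.

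**Step 3. The alternative reading.** If the 3 months were counted from the end of study (Day 30, 29 days after dosing), the reporting period would run to 29 + 90 = 119 to 29 + 92 = 121 days and would cover the 112 days. The text ties the 3 months to the last dosing, so this is not the natural reading.

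**Step 4. How many cases.** The documents give neither the number of women of childbearing potential nor a contraceptive failure rate, so both are assumed here. Expected conceptions in a 21-day gap = women × annual rate × 21/365.

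| Women (assumed) | 1% per year | 10% per year |
|---|---|---|
| 30 | 0.02 | 0.17 |
| 60 (every participant, an upper limit) | 0.03 | 0.35 |

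Across this range the most likely number is none.

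**The case against.** The strongest reply is that little would be lost. The Pregnancy Form depends on the investigator's awareness and has no time limit, and counselling, follow-up and newborn examination have none either. Section 8.8 also keeps a serious event reportable after its 30-day period if the investigator suspects a causal link, and Section 8.8.1 counts congenital anomaly and spontaneous abortion among pregnancy-associated serious events. This stands. A reader might infer that pregnancies in the last 3 weeks are not collected; the documents do not support that. They are unprompted, and could still be recorded if volunteered. Nor do the documents support saying that some will be missed, since Step 4 gives well under one expected case.

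A reader might also want to size the problem by the drug still present. Applying the 22-day half-life from dosing gives 91/22 = 4.1 half-lives and 5.7% remaining at 91 days, but that projects the terminal phase back to time zero. Section 2.1.5 predicts about 1% of Cmax at 672 hours (28 days) after 1280 mg. If a 22-day half-life is assumed from there, the level at 91 days is 1% × 2^(−63/22), about 0.14% of Cmax. The point should rest on the mismatch of periods, not on residual exposure.

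Finally, the instruction is delivered through consent, and the consent pages are not among the documents reviewed. Whether the information sheet carries the same 3 months cannot be checked. That limits what can be said about the sheet, but not about Section 8.8.1.

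**Conclusion.** The inconsistency is real and modest. For female participants, the instruction to report a pregnancy ends 20 to 22 days before the contraception period, with no scheduled visit after Day 30 to make up for it, and no section available for review closes the gap. The stated reason for the 16 weeks is also 28 days longer than the 16 weeks themselves (140 − 112).

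This rests on counting the 3 months from the single dose, as Section 8.8.1 says, and on 16 weeks as the operative contraception period. The gap would be 48 to 50 days if that period became 140 days, and would vanish if it were set at 3 months or less. Which duration is right is for the sponsor to settle.

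It might seem to follow that partner pregnancies need the same window. They do not: Section 8.8.1 sets no cut-off for them and Section 13.2.2 sets no contraception period for male participants, so applying the women's window could narrow what is collected.

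**What to change.** - Reconcile Section 8.8.1 with Section 13.2.2, and with inclusion criterion 4 (Section 5.2.1 and Synopsis), so that the instruction to female participants ends no earlier than the contraception period, whatever end date the sponsor confirms. Referring to that period by name, rather than by a separate number, would keep the two aligned.
- In the same revision, reconcile the 16 weeks with its stated reason and with the half-life in Section 2.1.3.
- Check that the participant information sheet matches, and correct it if it does not.
- Leave partner pregnancies without a cut-off.

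The alignment costs one phrase in the protocol and, if needed, the same phrase in the consent material. It adds no visit or test, and at most an occasional extra pregnancy form after the last visit.

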## 9 DESCRIPTION OF DATA MANAGEMENT

### 9.1 Specification of source documents

CRFs will be designed in collaboration between the site, sponsor and the contracted data management vendor (IQVIA), and will be used to record details of the trial and will serve as source documents for sponsor required data. The procedures for collecting the data are outlined in the respective data management manual / SOPs. Data in the individual participant files will include clinical information, blood sampling data for the specimens acquired to perform the different tests listed, and administrative information such as contact information. The forms will also include descriptions of AEs/ARs resulting in medical consultation or hospitalization. These forms, together with the investigator's notes, are considered to be source data. Additional hospital notes including laboratory reports and clinical notes in the event of emergency or hospitalization will also be collected and included as source notes.

### 9.2 Data management system

Data will be recorded using paper CRFs. The information will then be transcribed into the eCRFs within the electronic data capture system (eDC) by delegated data entry personnel. Data will be independently counter checked by study monitor(s) who will review the accuracy of data entry and transfer based on the study monitoring plan. The electronic system to be used will include only validated systems that are clinical trial compliant with audit trail capabilities.

### 9.3 Data security, access, archiving and back up

All source documents will be kept in each participant's folder. As required by the Tanzanian regulatory authority (TMDA), all records, documents and information related to this trial will be kept in safe custody at the clinical trial site for a period of not less than twenty years after study termination or premature termination of the clinical study.

## 10 STATISTICS

### 10.1 Hypothesis

This pilot BA/FE phase 1 trial is not designed to test specific hypotheses.

### 10.2 Determination of sample size

This is an exploratory trial to evaluate PK and safety of each treatment group and the sample-size is not based on formal statistical power. The number assigned to each treatment arm (n=12) is considered adequate to assess the trial objectives.

### 10.3 Description of statistical methods

The statistical methods and reporting will follow ICH E9 and international recommendations, including CONSORT.

### 10.4 Statistical Analysis Plan

A statistical analysis plan (SAP) containing detailed statistical methodology will be written and signed off before the database hard lock. The plan may be updated to reflect adaptive features of the trial as appropriate.

